Study design: Businesses are being actively recruited for this study. We aim to have a minimum of two outlets available for participants to visit. This study is a randomised controlled trial using a between-subjects design. Participants will be asked to visit a restaurant to eat lunch and complete some questionnaires. Participants will select one of the available restaurants to visit and will be randomly assigned to one of two conditions: Calorie labelling only or NS with calorie labelling. Later intake (over the rest of the day, after the lunch time study session) will be self-reported by participants. If one outlet is more popular than the other outlet(s), and we are not obtaining a similar number of participants for the outlets on offer, then we will actively recruit participants to each of the outlets to ensure a similar number of participants are recruited to each outlet tested.

Randomisation: Participants will be randomised to one of the two conditions. Data collection days at each of the outlets will be randomised as either NS with calorie labelling or calorie labelling only. Data collection days will be randomly assigned to condition using the RANDBETWEEN function in excel.

Sampling Plan

Existing Data: Registration prior to creation of data

Explanation of existing data: N/A

Sample

Data collection procedures: We will use an existing participant database consisting of local volunteer participants recruited through social media advertising. Only participants who have not taken part in previous similar research conducted by the appetite group at the University of Liverpool will be contacted. If required, more participants will be recruited from the local community (e.g. adverts on social media/posters in the university). Participants who sign up to the study can bring up to 4 guests with them to also take part. Tables of 5 participants were determined as the upper limit as it was deemed a manageable size for researchers to effectively monitor individual orders. Over the course of the study, we will attempt to ensure our sample is representative of the UK population in terms of gender (50% male, 50% female), age (36% aged 18-39; 64% aged 40+(31)), and SEP - education level (50% level 3 and above (2+ A-levels or equivalent, not including apprenticeships(32)).

Inclusion criteria:

- Can visit a restaurant in Liverpool city centre
- Regularly eat food prepared out of the home (from restaurants, cafes, fast food etc., at least once a month)

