Participants will be asked to complete a questionnaire on an iPad to collect demographic information, assess health food choice motives, PME relating to the menu labels and to guess the aim of the study. Participants will also be asked to confirm the food items they ordered, whether they had any additional components such as condiments, and to report whether they shared any items with others at the table and if so, how much was shared. Participants will be given clear examples of how to report this. Upon completion of the study session, participants will complete a payment form to receive monetary reimbursement. This reimbursement will compensate participants for travel and time.

The next morning, participants will be emailed with a link to Intake 24, an online programme for dietary recall. They will be asked to report anything that had been eaten after the lunch time meal the previous day. Following this, all participants will be fully debriefed.

The restaurants in which this study will take place will be independent restaurants in Liverpool city centre. As they are small, independent businesses, they are not required to report any nutritional information. Researchers liaised with restaurant owners, chefs and front of house staff to gather the required menu information (ingredients, cooking method) to calculate the nutritional content of meals using Nutritics(33), a platform which can be used to estimate the nutritional content of meals using validated methods. The NS values for all items on the food menus of the outlets were calculated using the NS spreadsheet available online (34). There are currently three outlets where data collection is planned to take place. These are all in Liverpool city centre and are 1) a plant-based café, 2) a café in the university campus and 3) a street-food inspired café.

Variables

Manipulated variables: Whether participants are provided with a calorie labelled menu or a menu where each item is also labelled with a NS classification from A (healthiest) to E (least healthy).

Adapted NS: The NS classification was created in France to apply to packaged food products, and the calculations are made based on energy, nutrients (saturated fat, sugar, salt, fibre, protein) and fruit, vegetable and nut content per 100g of the food product. Fruit, vegetable and nut content for each menu item was estimated by two researchers individually. Any disagreements were resolved by

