An adapted version of the University of North Carolina PME scale(38) will be used to measure health concern, product attitude, and discouragement of item consumption in response to the food menu. Participants will be given the menu they ordered from to look at. All participants will answer 3 questions using a Likert scale ranging from 1 - 5 anchored by "not at all" and "a great deal". The mean response to the three items will be calculated. PME is used as an early indicator of a health message's potential to change behaviour (e.g., reduce selection of less healthy items)(17). The scale has been used previously to identify the potential impact of food labels and is predictive of long-term behaviour (39-45).

NS label of each item selected (A,B,C,D,E).

A NS category value will be recorded for each item selected by participants.

Nutritional quality of each item and for the full meal

Nutritional quality for meal choices will be calculated using the UK NPM scoring system(46). This calculates a score (continuous variable) for a product by deducting a total score for positive nutrients from a total score for negative nutrients. A lower score represents greater nutritional quality and a higher score represents poorer nutritional quality.

We will calculate the mean NPM score weighted by energy content of items for each participant. This will ensure that the NPM score of main dishes will be weighted higher than that of starters or sides (assuming energy content of selected main is higher than any starters or sides), leading to a more representative overall NPM score for food orders. This will be done using the weighted.mean function in R(47). This function multiplies each value (i.e. NPM scores for individual items) by its corresponding weight (kcal content of individual items), sums all items and then divides this by the sum of the weights.

Energy content of all food ordered

The sum of energy (kcal) across all foods ordered for the meal will be calculated

Energy and nutrients consumed

Researchers will take pictures of plates before and after each item is given to participants. Researchers will estimate the percentage of each dish consumed, by estimating the percentage of individual meal components that have been eaten. Estimations will be guided by the information available from the nutritional analysis of items, which details the proportion of the meal that is made up by individual components. For example:

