Only participants who completed the restaurant visit (consumed a meal and completed the questionnaire) will be included in analysis. We will report analyses with any participants who guess the aims of the study included and excluded. We will identify any cases where the height and weight data provided has resulted in an implausible BMI value (<12kg/m² and >100kg/m²(49)) and exclude these subjects from analysis involving BMI.

Participant characteristics will be presented in a table. Data will include age, gender, ethnicity, BMI and highest education level. Continuous variables will be summarised by means and standard deviations, categorical variables will be summarised by counts and percentages. The descriptives table will report variables overall and split by condition and outlet.

Descriptive analyses:

We will report quantitative questionnaire findings and main outcomes by condition in a table. This will consist of: frequency of eating OOH food, health food choice motive scores, label awareness/understanding, PME, UK NPM score, kcal selected and consumed and the proportion of participants selecting food with each label (A-E). As above, these variables will be reported overall and split by condition and restaurant.

Anticipated primary analyses:

Shortly after starting data collection and prior to any interim analyses, we will finalise the full analysis plan and publish this alongside the protocol on the Open Science Framework. The anticipated analysis approach is briefly stated below.

PME

A linear mixed model will be used to assess the impact of labelling condition (calorie labelling only/NS with calorie labelling) on PME relating to the food menu (a mean score).

Nutritional quality of ordered meal (UK NPM score)

A further Linear mixed model will be conducted to explore the impact of labelling condition (calorie labelling only/NS with calorie labelling) on the nutritional quality of the participant's full meal (mean weighted UK NPM score: linear outcome variable).

Secondary analyses:

Likelihood of selecting a healthier option (A/B)

Any participants who have selected a healthier item (A/B) as part of their meal will be coded as 1 and participants who have only selected options with a C/D/E value will be coded as 0. We will conduct a logistic regression to test whether NS labelling (Y/N) is associated with the likelihood of selecting a healthier item.

Likelihood of selecting a less healthy option (D/E)

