Similar to the above, any participants who select a less healthy item (D/E) as part of their meal will be coded as 1, and participants who have only selected options with a A/B/C value will be coded as 0. We will conduct a logistic regression to test whether NS labelling (Y/N) is associated with the likelihood of selecting a less healthy item.

Energy and nutrient content consumed at lunch

Similar to primary analyses, we will explore the impact of NS labelling on total energy and nutrient content of food consumed (linear outcome variables) through n=8 linear mixed models. The nutrients explored will be salt, sugar, fat, saturated fat, protein, fibre and fruit vegetable and nut content.

Transformations: N/A

Inference criteria: Results for primary analyses will be considered significant at p<0.05, and to account for multiple comparisons, secondary analyses will be considered significant at p<0.01.

Data exclusion: If participants leave the restaurant study session without ordering food their data will be excluded from analyses.

Missing data: If participants do not complete the dietary recall survey, and therefore do not provide data of later intake, then we will impute the missing data for this variable. Any missing data for other outcomes (e.g., PME) will also be imputed. We will complete multiple imputation with 5 imputed datasets(50) in R using the 'mice' package. Imputation will be reported in line with published guidance(51).

Exploratory analysis:

Other:

Sample size:

We conducted a simulation to estimate sample size required for two primary outcomes: PME and NPM scores. Our simulation was based on previous research and knowledge of the outlets confirmed for data collection.

We simulated running the study with 20 participants a day for 20 days (400 total data points). For PME, we estimated from previous research that we may have an intercept PME value of 1.85 (SD: 1.08), with an intervention effect of 1 (the intervention group will have PME values 1 unit greater than the control group on average, based on previous research(52)), and minimal difference in PME

scores between the two outlets (0.2). We also assumed ICC of approximately 0.200, and a standard deviation of the random intercept of eating group in a mixed model of 1. Across 200 simulations using a regression model clustered by day, we would have 94% power (95% CI 89.75, 96.86) to detect differences in PME between the two conditions.

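### Limiting every analysis to questionnaire completers discards observed order data, including a primary outcome, and leaves the planned PME imputation little to act on

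*Protocol*

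**What the plan says.** Three statements in the protocol's Analysis Plan bear on who is analysed.

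- Under Participant characteristics: "Only participants who completed the restaurant visit (consumed a meal and completed the questionnaire) will be included in analysis". No outcome is exempted.
- Under Data exclusion: "If participants leave the restaurant study session without ordering food their data will be excluded from analyses". No other exclusion is listed there.
- Under Missing data, on the next-day recall: "If participants do not complete the dietary recall survey, and therefore do not provide data of later intake, then we will impute the missing data". Other outcomes are treated alike: "Any missing data for other outcomes (e.g., PME) will also be imputed". The method is multiple imputation with five datasets.

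The outcomes come from different sources.

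- PME comes only from the post-meal questionnaire: "Participants will be asked to complete a questionnaire on an iPad to collect demographic information, assess health food choice motives, PME relating to the menu". In Appendix D it is item 22, the last one.
- Nutritional quality comes from the items ordered: "We will calculate the mean NPM score weighted by energy content of items for each participant".
- Energy ordered has the same source: "The sum of energy (kcal) across all foods ordered for the meal will be calculated".
- Table size was capped at what was judged "a manageable size for researchers to effectively monitor individual orders". Plates are photographed before and after eating and filed by participant ID.

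**The concern.** Completing the questionnaire is something a participant does after being allocated and after reading the menu. Making it a condition of entry selects on a post-randomisation event. For outcomes that depend on the questionnaire, the data are simply missing and some rule is needed. For outcomes fixed when the order is placed, nothing is missing and the exclusion throws away observed values. One of these, the NPM score, is analysed as primary and used to size the trial.

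The rule also works against the protocol's own missing-data policy. PME is the example given of an outcome to be imputed. But the people most likely to lack it, those who stop before the last item, are removed before imputation can operate. Someone who skips the next-day recall, by contrast, is kept and imputed.

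At stake are the denominators of both primary analyses and some risk of selection if break-off differs by condition. The analysis set also needs to be settled before the interim look.

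**Working it through.** No figure in the protocol decides the point, so the first step is to follow one participant through the text.

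**1. A participant who orders and eats but stops the questionnaire before its last item**

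| Outcome | Source | Available? | Under the Participant characteristics rule | If all who ordered are kept |
|---|---|---|---|---|
| NPM score | items ordered and their kcal | yes | dropped | observed |
| A/B and D/E choice | items ordered | yes | dropped | observed |
| Energy ordered | items ordered | yes | dropped | observed |
| Energy and nutrients consumed | photographs, plus self-reported sharing and condiments | partly | dropped | photographs observed; self-report may be missing |
| PME | questionnaire item 22 | no | dropped | imputed |
| Later intake | next-day recall | possibly | dropped | observed or imputed |

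The first three rows are a loss of observed data. In the PME row the imputation policy is bypassed.

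**2. What is left for PME imputation.** Among people who completed the questionnaire, PME can be missing only if one or more of its three items was skipped in a submitted form. The protocol does not say that the imputation is meant only for that case.

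**3. How many people.** The maximum sample is 400 × 1.125 = 450, as the protocol states. The non-completion rate q is not given. For assumed values, 450 × q is:

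- q = 2%: 9 people
- q = 5%: 22.5, so about 22
- q = 10%: 45

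The Stopping rule section describes the interim sample as 224 participants with about 112 completers per condition, and 2 × 112 = 224. Targets may therefore be counted in completers. If so, the people dropped would come on top of 450 rather than out of it, but their order data would still be discarded.

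**4. How far the NPM contrast could move.** If a share q of one arm is dropped and those people differ from the retained by d standard deviations, that arm's mean moves by q × d × SD. The protocol gives SD = 3.29 and a planned effect of 0.22. With d = 0.5 (assumed) and loss in one arm only (assumed):

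- q = 2%: 0.02 × 0.5 × 3.29 = 0.033, or 15% of 0.22
- q = 5%: 0.05 × 0.5 × 3.29 = 0.082, or 37%
- q = 10%: 0.10 × 0.5 × 3.29 = 0.165, or 75%

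If the arms lose the same share and the dropped people differ from the retained equally, the two shifts cancel and the contrast does not move. These figures are one-sided illustrations, not estimates. They look large relative to 0.22 mainly because the planned effect is only 0.22 / 3.29 = 0.07 SD.

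**The case against.** The best defence is that the statements can be read together. A reader might infer that the protocol gives two contradictory exclusion rules. The text does not support that. The Data exclusion paragraph names one excluded group and does not say it is the only one, and everyone it excludes is already outside the completer set. It is redundant rather than contradictory. Likewise, PME imputation is not wholly blocked, since it can still fill skipped items, and imputing later intake raises no conflict because the recall falls after the restaurant visit. All of this stands. It does not rescue the discarded order data, which are lost on any reading.

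A reader might also infer that every food outcome is fixed by the order and the photographs. That is too strong. The estimates of the proportion eaten take self-reported sharing into account, and the questionnaire also records condiments and confirms the items ordered. Intake at lunch therefore cannot be derived exactly as planned without it. The claim is limited to NPM, A/B and D/E choice and energy ordered.

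PME's last place rests on Appendix D. The lists in the Procedure and Study flow sections mention it earlier, but they need not be in order of administration, and the questionnaire itself is the more specific source.

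Finally, the loss may be negligible: the questionnaire is completed on a supplied iPad straight after the meal, and the payment form comes afterwards. Both arms get the same questionnaire, so nothing in the document points to differential break-off. This is a fair argument about size, and it stands.

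**Conclusion.** The point holds in limited form. The protocol sets a post-randomisation, post-exposure exclusion that discards observed data on NPM, food choice and energy ordered for anyone who orders but does not finish the questionnaire. It also leaves the stated PME imputation with little to do.

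The size is unknown and probably small. The 9 to 22 people rest on an assumed 2% to 5% non-completion. The shifts of 15% to 37% of the planned NPM effect also assume loss in one arm only and a half-SD difference, neither of which the document supports. A reader should not infer that the trial's result is likely to be materially biased.

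This is a stated rule rather than a detail left to a later analysis plan. The case for changing it is that it gains nothing for the order-based outcomes and is easily corrected.

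**What to change.** Replace the entry condition under Participant characteristics with a rule along these lines:

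- NPM, A/B choice, D/E choice and energy ordered: analyse everyone who ordered food, by the condition allocated to that day.
- PME: use the same set, with missing PME imputed as the Missing data paragraph already provides. State that this covers both skipped items and unfinished questionnaires.
- Energy and nutrients consumed: use the same set and the plate photographs. Where sharing or condiment reports are missing, impute them or state the assumption made.
- Keep the questionnaire-completer set as a sensitivity analysis, and report by condition how many people ordered but did not complete.

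The protocol says the full analysis plan will be finalised before any interim analysis. The change should be made by then, so that the denominator is not chosen after results are seen. For the order-based outcomes and PME it costs about a sentence. The intake outcomes need one further stated rule. No additional data are collected.

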Recruitment	 Participants will be identified via an existing database of individuals who expressed interest in taking part in research or through social media advertisement. Prospective participants will be emailed with a brief study overview (consumer behaviour at different restaurants) and a link to complete the screening questionnaire (Appendix A). Throughout the study (e.g. after 25%, 50% and 75% completion achieved), we will examine the characteristics of participants to ensure the sample is broadly representative of the UK population. If this is not the case (e.g. there are 70% female participants) then recruitment will be altered to source the participants needed (i.e. to recruit an equal number of male participants). This will be done through targeted advertising.
Information sheet	Eligible participants will be e-mailed an information sheet
and informed	(Appendix B) and consent form (Appendix C). Participants will be
consent	told they can ask any questions about the study via e-mail.

Meal choice task	 The researcher will schedule a study visit day. For each of the restaurants, there will be 6 available lunch time study slots scheduled every 30 minutes between 12pm and 2.30pm. Participants may bring a maximum of four guests aged 18 ye older to the restaurant, and must confirm the final number participants, and that all guests meet inclusion criteria. As the additional guests would not have received an online information sheet and consent form, upon arrival at the restaurant all participants will be provided with information the researcher and will give verbal consent. The researcher answer any questions prior to the study. Study days will be randomised as calorie labelling only or NS calorie labelling condition. Participants will be given a participant number which must entered in the follow-up questionnaire they complete. 				

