For NPM scores, we calculated using the two confirmed outlet menus, that we may have an intercept NPM score of -0.27 (SD: 3.29) with an intervention effect of 0.22 (the intervention group will select meals with with greater nutritional quality, shown by a 0.22 higher NPM score) based on previous research(26) and a mean difference between the two outlets of 1.4 (the difference in mean NPM scores for the two outlets). We also assumed ICC of approximately 0.819, and a standard deviation of the random intercept of eating group in a mixed model of 1. Across 200 simulations using a regression model clustered by day we would have 88.5% power (95% CI 83.25, 92.57) to detect differences in NPM scores between the two conditions.

Due to uncertainty over size of anticipated effects and available resources, we will increase the above desired maximum sample size (400) by 12.5% to 450 participants.

Stopping rule

Prior to the study we do not know with certainty what the rate of participant recruitment will be, and effect size estimates have a degree of uncertainty. To balance the trade-off between costs (e.g., in research time, participant burden) and likelihood of the study providing convincing evidence, we will conduct interim analyses to assess whether the results are convincing enough to conclude that effects on PME and nutritional quality of food order are present(53). The interim analyses will examine the effect sizes of these two primary outcomes and observed statistical significance. We will also calculate Bayes Factors to assess the strength of evidence for the experimental vs null hypotheses.

We will conduct the interim analysis when we have obtained approximately 50% of the full sample (224 participants, ~112 completers in each condition). If at this point, the data suggests that it is extremely unlikely that either of the predicted effects would be observed up to maximum sample size capacity (described above), and if Bayes Factors suggest there is evidence for the null hypothesis (BF10 < 0.3) then we will cease data collection and conduct full planned analyses.

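### Menus are randomised by study day, but A/B and D/E selection are to be analysed by a logistic regression that ignores day, table and outlet, so the 1% test does not hold its level

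*Protocol*

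**What the plan says.** **Allocation.** The Randomisation paragraph first says that participants are randomised, then sets out how: "Data collection days will be randomly assigned to condition using the RANDBETWEEN function in excel". The meal choice task in Study flow agrees: "Study days will be randomised as calorie labelling only or NS calorie labelling condition". Everyone who attends on a given day therefore gets the same menu. Guests are allowed, with at most five people at a table.

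**Binary outcomes.** Under Secondary analyses, A/B selection is covered by "We will conduct a logistic regression to test whether NS labelling (Y/N) is associated with the likelihood of selecting a healthier item", and D/E selection by "We will conduct a logistic regression to test whether NS labelling (Y/N) is associated with the likelihood of selecting a less healthy item". Neither entry names a random effect, a clustered standard error or an outlet term. Together they test the fourth hypothesis.

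**Other outcomes.** PME and NPM score each get a linear mixed model. Energy and nutrients consumed are analysed "through n=8 linear mixed models".

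**Sample size.** The simulation has 20 days of 20 people and a random intercept for eating group. For PME it reports: "Across 200 simulations using a regression model clustered by day, we would have 94% power". For NPM it also assumes "a mean difference between the two outlets of 1.4".

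**Threshold.** Under Inference criteria, "secondary analyses will be considered significant at p<0.01".

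**The concern.** The day is the unit that is randomised, so the evidence about the menu comes from roughly 20 independent allocations rather than from 400 to 450 separate diners. Two things make diners alike within those units:

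- People eating on the same day share specials, stock, staff and weather.
- People at the same table influence each other's orders.

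An ordinary logistic regression on condition counts each diner as independent information. Its standard error is then too small, its confidence interval too narrow and its p-value too low.

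Outlet adds to this. Study days are run at particular outlets, and the plan's own inputs have the outlets differing in nutritional quality. If days are assigned by an unconstrained random draw, the arms can differ by chance in their mix of outlets, and a model without outlet reads that as noise-free signal.

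At stake is a false claim that Nutri-Score labels shift diners towards healthier items or away from less healthy ones.

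**Working it through.** **Inputs from the protocol.** Day as unit of allocation; 20 diners per day; about 20 days; maximum 450 participants; tables of at most 5; secondary threshold 0.01 (taken as two-sided); outlet gap 1.4 NPM points; NPM SD 3.29.

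**Assumed.** The ICC for A/B or D/E selection, the share choosing the item, and the usual table size. None is given.

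**Step 1: formula, ICC on the observed 0/1 scale.** With m people per cluster, the design effect is DEFF = 1 + (m − 1) × ICC. The true error of a nominal 1% test is 2 × [1 − Φ(2.576/√DEFF)]. At ICC = 0 this returns 1.0%, so the stated threshold is reproduced only under independence.

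Example: m = 20, day ICC 0.05. DEFF = 1 + 19 × 0.05 = 1.95; 2.576/√1.95 = 1.84; true error 6.5%.

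| Day ICC (m = 20) | DEFF | True error |
|---|---|---|
| 0.005 | 1.095 | 1.4% |
| 0.01 | 1.19 | 1.8% |
| 0.02 | 1.38 | 2.8% |
| 0.05 | 1.95 | 6.5% |
| 0.10 | 2.90 | 13.0% |

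Table clustering only, tables of 5: ICC 0.05 gives DEFF 1.20 and 1.9%; ICC 0.20 gives DEFF 1.80 and 5.5%.

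**Step 2: simulation, ICC on the latent scale.** Settings: 11 v 11 days of 20 diners, 30-50% choosing the item, Wald test of the log odds ratio, 40,000 trials per setting. Independent data give 0.9%. A latent-scale ICC corresponds to a smaller observed-scale ICC, so these figures are lower than those in step 1.

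| Clustering | ICC | True error of nominal 1% test |
|---|---|---|
| Day only | 0.01 | 1.4-1.5% |
| Day only | 0.02 | 2.0-2.3% |
| Day only | 0.05 | 4.4-4.9% |
| Day only | 0.10 | 8.7-9.6% |
| Table only, tables of 2 / of 5 | 0.05 | 1.0-1.1% / 1.5-1.6% |
| Table only, tables of 2 / of 5 | 0.10 | 1.3% / 2.2-2.4% |
| Table only, tables of 2 / of 5 | 0.20 | 1.5-1.6% / 3.6-3.9% |

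Both kinds together: tables of 2 at 0.1 plus day 0.01 give 2.0%; tables of 4 at 0.2 plus day 0.05 give 7.5%. Coverage of a nominal 95% interval is about 93% at day ICC 0.01, 86-87% at 0.05 and 79-81% at 0.10.

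**Step 3: outlet omitted, no other clustering.** The standardised gap is 1.4/3.29 = 0.43 SD. If A/B choice differed by as much (an assumption), that is about 40% v 60% at two outlets. With days assigned by independent coin flips, the true error is 4.8%; at half the gap it is 1.6%.

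**Step 4: do the remedies hold 1%?**

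- Day-level proportions regressed on condition and outlet, t on days − 3 df (two outlets): 0.9-1.1%.
- Logistic GEE clustered by day, with outlet: 2.1-2.7% with uncorrected robust errors and a normal reference; 0.7-1.4% with bias correction and a normal reference; 0.4-0.7% with bias correction and a t reference.
- A normal cut-off is not safe with so few days: with 20 days in two arms, P(|t| > 2.576) on 18 df is 1.9%.
- Mixed-effects logistic regression was not simulated.

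**The case against.** The strongest reply is that the analysis text calls itself brief and anticipated, with a full plan to follow before any interim analysis, and that random effects and covariates are ordinarily settled there. The linear mixed models do not name their random effects or an outlet term either. That is fair as far as it goes, and the missing outlet term is not peculiar to the logistic models. But the protocol names a model class for each outcome it models. It picks one that carries clustering for every continuous outcome and one that does not for these two. That is a stated choice, and the provisional status means only that it is easy to correct.

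Three further points stand as limits:

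- **Size is unknown.** With small tables and weak clustering the inflation is negligible. The larger figures need a day-level ICC of 0.05 or more. The ICCs in the sample-size section (0.200 and 0.819) are for PME and NPM, with the level unclear, and are not borrowed here.
- **The outlet figure is conditional.** The 1.4 gap was calculated from menus, not from diners' orders, and A/B labels also depend on the kcal adjustments. If days were balanced within each outlet, omitting outlet would not inflate the error (about 0.9%). The protocol describes a RANDBETWEEN draw and states no such constraint.
- **These are secondary outcomes.** Sample size and the stopping rule do not depend on them.

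**Conclusion.** The concern holds. As written, the A/B and D/E analyses treat a day-randomised design as if diners had been randomised one by one. The direction is certain: any positive correlation within day or table puts the true error above 1%. The amount is not. It runs from negligible (1.0-1.1% for tables of 2 at a table ICC of 0.05) to several-fold (8.7-9.6% at a day ICC of 0.10), assuming about 20 diners per day, 30-50% choosing the item and latent-scale ICCs. An unbalanced mix of outlets could bring it to 4.8% by itself under the assumed 40% v 60% gap. This should be corrected before the full plan is published; it does not touch the primary outcomes.

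**What to change.** Replace the model sentence in both entries under Secondary analyses with wording such as:

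> Selection of an A/B item and, separately, of a D/E item will be analysed by logistic GEE with condition and outlet as covariates, clustered by study day (which contains the tables), using bias-corrected robust standard errors and a t reference based on the number of days.

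Either of two alternatives would also do:

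- a regression of day-level proportions on condition and outlet, with t on the day degrees of freedom;
- a mixed-effects logistic regression with random intercepts for day and table, also with small-sample inference based on days.

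An outlet term alone is not enough, because the randomised unit is the day.

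**Cost.** Plan wording and a different model call. Visit date, outlet and table must be stored with the participant number; visits are already booked by date and time. Confidence intervals for these outcomes will be wider, and the bias-corrected GEE with a t reference is slightly conservative (0.4-0.7% at a nominal 1%).
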